Early Treatment of Cytokine Storm Syndrome in Covid-19

NCT04362111

UAB IRB Final Approval Date: July 28 2020

Protocol

Introduction

Macrophage Activation Syndrome (MAS) or Cytokine Storm Syndrome (CSS) is a disorder consisting of massive systemic inflammation, multi-organ system failure, disseminated intravascular coagulopathy, and often severe morbidity/mortality. Reports from areas initially impacted by Covid-19 confirm clinical and laboratory features present in patients with respiratory failure that are identical to those associated with Cytokine Storm Syndrome (CSS) occurring in the setting of other disorders and viral infections (1,2). The recombinant human IL-1 soluble receptor antagonist (rhIL-1ra) anakinra has a short half-life of 4-6 hours, is quick acting and in multiple case reports/series has been reported to be safe as well as effective in treating CSS occurring in the setting of herpes virus infections (EBV/CMV/HSV), ehrlichiosis, sepsis syndromes, adult Still disease/systemic JIA, and systemic lupus (3-6). In children with severe flares of sJIA, doses as high as 100 mg sc every 6 hours have been employed with success (7) and in the absence of significant noted toxicities. In previous trials of anakinra use for management of sepsis, doses up to 3500 mg/day were employed over 72 hours without any noted serious toxicities attributed to anakinra (8). In a recent study examining outcomes in the phase III sepsis trials, treatment with anakinra was associated with improved survival in a subgroup with MAS attributes including hepatic dysfunction and coagulopathy (4) Trials of anakinra to treat CSS in hospitalized patients with Covid-19 infection and features of CSS are therefore warranted.

Specific Aims

The specific aims of the trial are to determine whether treatment with anakinra added to standard of care treatment for hospitalized patients with Covid-19 pneumonia results in:

1. . Survival and discharge from the hospital without the need for intubation/mechanical ventilation. (Primary outcome)
 1. No increase in oxygen requirement or oxygen delivery measures to maintain $\text{SaO}_2 > 90\%$ at 48 hours compared to baseline at study entry/randomization. (Primary outcome)
 2. No increase in oxygen requirement or oxygen delivery measures to maintain oxygen saturation $>90\%$ Day 2 (48 hours) through Day 105 (120 hours). (Secondary outcome)
 3. At least 25% decrease in serum ferritin, LDH, CRP, and d-dimer at 48 hours. (Secondary outcome)
 4. Normalization by Day 5 of laboratory CSS attributes: ferritin, fibrinogen, AST, ALT, leucopenia, tryglycerides, sCD25 (Secondary outcome)
 5. Normalization or $\geq 75\%$ improvement by Day 10 (120 hours) in each of the following laboratory CSS attributes elevated beyond the normal range at randomization: ferritin, fibrinogen, AST, ALT, leucopenia, thrombocytopenia, d-dimer, CRP, triglycerides, sCD25. (Secondary outcome)
 6. Decreased time to achievement of $\geq 93\%$ oxygen saturation on room air. (Secondary outcome)
 7. No increased prevalence of nosocomial bacterial or fungal or viral infection through the time of hospital discharge. (Secondary outcome)
 8. No failure to develop neutralizing antibody to Covid-19 measured at Day 28. (Secondary outcome)
5. Discharge from hospital without the need for intubation/mechanical ventilation. (Secondary outcome)

Significance

If shown effective, early identification of CSS and repurposing anakinra for its treatment in severe Covid-19 illness will help reduce ICU admissions, improve patient outcomes and enhance survival.

Confirmation of a genetic basis for susceptibility to Covid-19 associated CSS as we identified in H1N1 associated deaths (6) will also facilitate risk stratification and future targeted approaches to Covid-19 disease management.

Design

Recruitment and Enrollment: Thirty patients will be recruited for enrollment; potential subjects will be identified from the registry of Covid-19 patients admitted to the University of Alabama Hospital.

Patient Compensation: Not applicable

Eligibility/Inclusion Criteria:

Inclusion criteria:

1. 18 years old or older
2. Molecular diagnosis of SARS-CoV-2 infection and Covid-19 pneumonia
3. Radiographic imaging consistent with Covid-19 pneumonia
4. Room air oxygen saturation <93%
5. Hyperferritinemia (>700 ng/ml)
6. Any three of the following:
 - a. elevated d-dimer (> 500 ng/ml)
 - b. thrombocytopenia (< 130,000/mm³)
 - c. leucopenia (WBC < 3500/mm³) or lymphopenia (<1000/mm³)
 - d. elevated AST or ALT (> 2X ULN)
 - e. elevated LDH (> 2X ULN)
 - f. CRP > 100 mg/L

Exclusion criteria:

1. Participation in other investigational treatment protocols for Covid-19 infection
2. Culture confirmed active bacterial infection requiring antibiotic therapy
3. On mechanical ventilation
4. Previous known hypersensitivity reaction to anakinra
5. Previous known hypersensitivity reaction to E Coli derived proteins
6. Pregnant or breast-feeding females

Subjects in the SoC only arm with deterioration of respiratory parameters and CSS markers at 48-96 hours will be transitioned to treatment with anakinra. Patients will stay on anakinra until all CSS markers no longer exceed the thresholds required for enrollment or through Day 5 of anakinra treatment, whichever comes first. Anakinra may be continued after Day 5 of treatment at the discretion of the treating physicians.

Informed Consent:

Identified patients who may be eligible for enrollment will be asked to consider participation in the protocol in the context of the informed consent process whereby the risks and benefits of their participation are discussed with a study investigator. As subjects with CSS/MAS are often severely ill,

those with any suspected altered sensorium will not be enrolled without the assent of a family member who is the designated representative of the patient to assist with their decision whether or not to participate.

Randomization:

Randomization will be assigned by the study coordinator using a computer-based randomization algorithm. The respective PIs will remain blinded to treatment group assignment for all subjects until study completion.

Visit Schedule and Study Procedures

Following obtaining informed consent and 1:1 randomization by computer, study assessments will be as follows:

Day 0:

- Record vital signs, ventilation and oxygen support, heart function, and kidney function/support.
- Blood drawn for these tests:
 - ferritin, CBC with diff, CMP, ESR, CRP, fibrinogen, D-dimer, INR/PT, LDH triglyceride level
 - Cytokine-12 panel, IL-18, CXCL9, sCD25, sCD163, IL-1 β , NK/B/T-cell lymphocytes
 - NK cell function assay
- Blood sample for genetic testing for perforin pathway (genetic traits associated with CSS)

Every effort will be made to procure remdesivir as available under existing PUA for all enrolled subjects.

Following completion of the baseline assessments, dosing of study agent (100 mg anakinra or equal volume saline placebo) will commence every 6 hours by subcutaneous administration.

Day 1-Day 9:

- Record vital signs, ventilation and oxygen support, heart function, and kidney function/support.
- Blood drawn for these tests: ferritin, CBC with diff, CMP, ESR, CRP, fibrinogen, D-dimer, INR/PT, LDH

Day 10:

- Record vital signs, ventilation and oxygen support, heart function, and kidney function/support.
- Blood drawn for these tests:
 - ferritin, CBC with diff, CMP, ESR, CRP, fibrinogen, D-dimer, INR/PT, LDH, triglyceride level
 - Cytokine-12 panel, IL-18, CXCL9, sCD25, sCD163, and subsets of NK/B/T-cell lymphocytes

If after Day 5 but before Day 10, lab studies show that the levels of ferritin, d-dimer, CRP, LDH, AST, ALT have all returned to normal or improved $\geq 75\%$ from noted Day 0 elevations in these laboratory tests AND the subject has $\geq 93\%$ saturation on room air oxygen, the dose of IP will be decreased to twice daily until Day 10.

All study participants will continue to receive current standard of care treatment for Covid-19 infection. It is understood the standard is evolving and that some treatments that are newly considered standard of care (such as remdesivir) may not be available to enrolled subjects.

Withdrawal of Participant Consent and Discontinuation of Study Drug:

Study participation may be discontinued for any of the following reasons:

- a. Subject decision to withdraw consent for study
- b. Evidence of allergy to administered anakinra
- c. Intolerable adverse event as judged by study investigator and participant
- d. Decision to terminate the study by the investigator and the DSMB due to one or more of the following:
 - Death in any subject in which the cause of death is judged to be probably or definitely related to the study drug by the treating investigator.
 - The occurrence in any subject of a life-threatening SAE whose causal relationship to study drug is judged to be probable or definite by the treating investigator.
 - Two occurrences of Grade 3 or higher toxicities (per NCI CTCAE) that are assessed to be related to the study drug by the investigator.
 - Two occurrences of a clinically significant Grade 3 or higher laboratory abnormality (per NCI CTCAE) assessed to be related to the study drug by the investigator.

If the study drug is discontinued, unless the subject withdraws consent, the subject will be followed for the full treatment/observation period (through Day 60) and all data will be collected as scheduled.

If the study drug is discontinued, unless the subject withdraws consent, the subject will be followed for the full treatment/observation period and all data will be collected as scheduled.

Data Collection:

Clinical and laboratory data as described in 6.1.4.1. as well as concomitant meds, duration of ICU stay, duration of hospitalization and any noted adverse events, will be collected and stored on a secure UAB server. The data will be de-identified, referenced to the assigned study subject number only.

Safety Data and Adverse Events:

An adverse event (AE) will be defined as any untoward medical occurrence in a patient or clinical investigation subject administered anakinra or placebo during the study, and which does not necessarily have to have a causal relationship with this treatment. An AE will therefore be any unfavorable and unintended sign (including an abnormal laboratory finding, for example), symptom, or disease temporally associated with the use of anakinra/placebo, whether or not considered related to the medicinal product. All treatment emergent AEs will be recorded on source documents (i.e. original documents, data, and records). AEs include those reported spontaneously by the subject and those noted incidentally or as observed by the investigator or study personnel. To avoid vague, ambiguous, or colloquial expressions, the AE will be recorded using standard medical terminology that is as specific as possible, rather than the subject's own words. Whenever the investigator is confident in making a unifying diagnosis, all related signs, symptoms, and abnormal test results will be grouped together and recorded as a single AE.

All clinically significant abnormalities noted upon physical examination, or other diagnostic test results will be reported as an AE, except for baseline measurements that may be considered part of the medical history. In addition, all clinically significant AEs that continue at Study Termination will be followed up by the investigator and evaluated with additional tests if necessary, until the underlying cause is diagnosed or resolved, or is determined to have resolved with sequelae. All AEs will be evaluated for intensity and causal relationship with use of the study medication (or study procedures if applicable) by the investigator.

AEs that occur following completion of study termination/early termination procedures will be recorded on a designated AE page of the source documents only if the investigator considers the event as clinically significant and as related to study medication or study procedures.

All adverse events that are deemed to be serious and meet the definitions provided in section 6.1.5.2, for serious adverse events will be reported as SAEs.

SAEs

Any AE that results in any of the following outcomes will be considered an SAE, as per outcomes as defined according to Code of Federal Regulations (CFR) Title 21 part 312.32.

- Death
- Life-threatening situation (subject was at risk of death at the time of the event. This does not refer to an event that might have caused death if it was of greater intensity.)
- Prolongation of existing hospitalization
- Persistent or significant disability or incapacity
- Congenital anomaly or birth defect
- Important medical events that may not result in death, be life-threatening, or require hospitalization but may jeopardize the subject and may require medical or surgical intervention to prevent one of the above outcomes (based upon appropriate medical judgment)

A data safety monitoring board (DSB) comprised of three UAB Rheumatologist, a UAB pulmonary and critical care specialist, a UAB specialist in infectious disease, UAB specialist in hematology, and a UAB specialist in nephrology will meet following enrollment of the first 15 subjects or quarterly to review inter-current study outcomes and safety data. The DSB for this study will also review any and all deaths that occur during the study within two weeks of the time of death. If it is the assessment of the DSB that deaths or other SAEs during the course of the study are significantly more prevalent in the anakinra treatment arm or the placebo arm, the study will be prematurely terminated.

Statistical Analysis Plan

The primary efficacy analysis will be conducted on a modified intention-to-treat basis and defined as all patients who underwent randomization and received either anakinra or placebo before intubation/mechanical ventilation or death. Descriptive statistics will be used to characterize participants. Continuous data will be summarized by means and standard deviation (SD) and analyzed by student t tests. Categorical data will be described with frequencies and percentages and compared using Fisher's exact or chi square tests. Cox proportional hazards models will be used to calculate hazard ratio for the association between treatment group and death from any cause or need for mechanical ventilation; due to small sample size control for demographic characteristics, clinical variables and comorbidities will likely not be possible. Calculated 95% confidence interval (CI) and $p < 0.05$ will be considered significant. All analysis will be conducted with SAS v 9.4 (Cary, NC, USA).

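### The nosocomial infection comparison (Specific Aims, sub-aim 7) mixes daily infection risk with length of stay; a rate per inpatient day should be reported beside the crude proportion

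*Combined protocol and SAP*

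**What the plan says.** Sub-aim 7 under Specific Aims is a secondary outcome: "No increased prevalence of nosocomial bacterial or fungal or viral infection through the time of hospital discharge". The Statistical Analysis Plan does not mention infection by name. Its general rule for categorical data is frequencies and percentages with Fisher's exact or chi-square tests. Its only time-to-event model is a Cox model for death or mechanical ventilation. It specifies no infection rate per patient-day, no common infection window and no treatment of death as a competing event.

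Two efficacy aims bear on how long patients stay. The primary outcome is "Survival and discharge from the hospital without the need for intubation/mechanical ventilation", and sub-aim 6 is "Decreased time to achievement of $\geq 93\%$ oxygen saturation on room air".

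On size, the Design section states "Thirty patients will be recruited for enrollment", and allocation is 1:1, so about 15 per arm. On the threshold: "Calculated 95% confidence interval (CI) and $p < 0.05$ will be considered significant".

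The Data Collection paragraph says that duration of hospitalization and adverse events are collected. Under Safety Data and Adverse Events, all treatment-emergent events are recorded whatever their cause. Once study termination or early termination procedures are complete, events are recorded "only if the investigator considers the event as clinically significant and as related to study medication or study procedures".

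**The concern.** Sub-aim 7 is a safety question about an immune-modulating drug, and its observation window is set by an event after randomization that the drug might influence. A crude proportion infected by discharge depends on two things: how often infections occur per day in hospital, and how many days patients spend there. Fisher's test on the proportions cannot tell them apart. If anakinra patients left sooner, a higher daily infection rate would look smaller than it is, or could vanish. If they stayed longer, for instance because more of them survived a severe illness, an unchanged daily rate could look like harm. In either case a conclusion on the infection aim could reflect length of stay and not the drug's effect on infection risk.

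**Working it through.** The plan states no infection rate, length of stay, margin or power, so there is no figure of its own to reproduce. The check asks how the planned comparison behaves over a range of stays.

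**Inputs.** From the documents: window ends at discharge; crude proportions compared; 30 patients randomized 1:1; threshold 0.05 (taken as two-sided). Assumed: a constant control rate h = 0.02 infections per inpatient day (range 0.01 to 0.03), a true rate ratio RR of 1.5 or 2.0, and a control stay of 14 days.

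**Formula.** For a stay of L days, the proportion infected by discharge is 1 − exp(−h × RR × L), with RR = 1 for control.

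Control, 14 days: 1 − exp(−0.02 × 14) = 1 − exp(−0.28) = 24.4%.

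| Anakinra stay (days) | Stay ratio | RR 2.0 | RR 1.5 |
|---|---|---|---|
| 14 | 1.00 | 1 − exp(−0.56) = 42.9% | 1 − exp(−0.42) = 34.3% |
| 12 | 0.86 | 1 − exp(−0.48) = 38.1% | 1 − exp(−0.36) = 30.2% |
| 10 | 0.71 | 1 − exp(−0.40) = 33.0% | 1 − exp(−0.30) = 25.9% |
| 7 | 0.50 | 1 − exp(−0.28) = 24.4% | 1 − exp(−0.21) = 18.9% |

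**Break-even.** The proportions are equal when h × RR × L(anakinra) = h × L(control), that is, when the stay ratio is 1/RR: 0.50 for a doubled rate and 0.67 for a 1.5-fold rate. The base rate h cancels, so repeating the sum at 0.01 or 0.03 does not test the result. What matters is the stay ratio against the rate ratio. Exponentially distributed stays in place of fixed ones give nearly the same risk ratios.

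**Opposite direction.** With no drug effect (RR = 1) and stays of 14 versus 20 days, the proportions are 24.4% versus 1 − exp(−0.40) = 33.0%, an apparent excess produced by stay alone.

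**What a rate recovers.** Take RR 2.0 with 14 versus 7 days, where the proportions are identical. Expected first infections are 15 × 0.2442 = 3.66 in each arm. Expected days at risk are 15 × 0.2442/0.02 = 183.2 (control) and 15 × 0.2442/0.04 = 91.6 (anakinra). The rates are 2.0 and 4.0 per 100 inpatient days, ratio 2.0. The standard error of the log ratio is about √(1/3.66 + 1/3.66) = 0.74, so the 95% interval multiplies and divides the ratio by exp(1.96 × 0.74) ≈ 4.3: roughly 0.47 to 8.5.

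**What a common 28-day window recovers.** Suppose the post-discharge rate is 25% of the inpatient rate, with stays of 14 versus 7 days. Control: 1 − exp(−(0.28 + 0.005 × 14)) = 29.5%.
- If the doubled rate persists after discharge, anakinra is 1 − exp(−(0.28 + 0.01 × 21)) = 38.7%.
- If the drug excess ends at discharge, anakinra is 1 − exp(−(0.28 + 0.005 × 21)) = 32.0% at RR 2.0, and 1 − exp(−(0.21 + 0.105)) = 27.0% at RR 1.5, still reversed.
- If the post-discharge rate is zero, the longer window changes nothing.

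**Power.** With 15 per arm, Fisher's test reaches p < 0.05 only at splits such as 5 v 0, 7 v 1, 9 v 2 or 10 v 3. Even with equal 14-day stays and a doubled rate, exact power is 5.2% to 12.1% for h from 0.01 to 0.03.

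**The case against.** The strongest defence is that the window suits the endpoint. Nosocomial infection is acquired in hospital, so fewer infections through fewer hospital days is a real benefit, and the crude proportion measures that net burden. This stands, and it is why the crude proportion should be kept. It does not answer whether each day in hospital is riskier on anakinra, which a reader of a safety aim also needs to know.

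Second, a shorter stay is an inference. The primary outcome concerns discharge without ventilation, not time to discharge; sub-aim 6 concerns oxygen saturation. The schedule also runs daily blood tests and dosing to Day 10, which fits uneasily with assumed stays of 7 to 9 days. This stands as well: the direction and size of any distortion are unknown in advance.

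Third, a reader might infer from the adverse event section that infections appearing after discharge are discarded unless judged related to treatment. The text does not support that. The relatedness condition begins after study termination procedures, not at discharge, and before that point events are recorded whatever their cause. The gap lies in how sub-aim 7 is defined and analysed, not necessarily in what is collected.

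Fourth, 15 patients per arm and no stated margin limit this aim more than the window does. True: a non-significant test could not establish the absence of an increase under any window. But the estimates will still be read for safety, and an estimate that is imprecise need not also be distorted.

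**Conclusion.** The point holds as a limited, inexpensive correction. Sub-aim 7 as analysed confounds daily infection risk with days at risk whenever the arms differ in length of stay, and nothing in the SAP separates them.

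A reader might go further and conclude that a finding of no increase is to be expected even if anakinra raises the daily rate. The arithmetic does not support that in general. Full masking needs a stay ratio near 1/RR. Cutting stay from 14 to 12 days leaves most of a doubled rate visible (24.4% versus 38.1%), and 14 to 10 days leaves part of it (24.4% versus 33.0%), although a 1.5-fold rate is then nearly hidden (24.4% versus 25.9%).

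The illustrations rest on an assumed constant daily rate and assumed stays. The structural point does not depend on those values, only on the arms differing in length of stay. If daily risk changes over the course of a stay, a rate per inpatient day is a summary and not an exact correction.

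**What to change.** Keep the crude proportion infected by discharge, labelled as the net-burden measure. Add nosocomial infections per 100 inpatient days at risk by randomized arm, counting each patient's first infection and ending time at risk at infection, discharge or death, with a rate ratio and 95% confidence interval. State that any conclusion on sub-aim 7 rests on both measures. Hospitalization duration and adverse events are already collected, so the cost is one table and a sentence in the SAP; infection onset dates must be available from the adverse event record.

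As an optional supplement, report all new bacterial, fungal or viral infections through a common Day 28 regardless of judged relatedness. Day 28 is already the antibody time point; Day 60 appears only in the paragraph on discontinuing study drug. This count would need a post-discharge infection check, would rely on records or patient report, and would include some infections that are not nosocomial. It should not replace the rate, since it corrects little if risk after discharge is low.

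The intervals will be wide at about 15 per arm, and the report should say so and not read a non-significant result as absence of an increase.

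### The Day 28 neutralizing antibody outcome is recorded only as yes/no, so with about 15 patients per arm a moderate general lowering of titre would often be missed; a titre comparison should be added beside it.

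*Combined protocol and SAP*

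**What the plan says.** Specific Aims, sub-aim 8, gives the outcome as "No failure to develop neutralizing antibody to Covid-19 measured at Day 28. (Secondary outcome". No titre, assay, positivity cutoff or margin appears anywhere in the document.

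Under Recruitment and Enrollment, "Thirty patients will be recruited for enrollment", and the visit schedule specifies "1:1 randomization by computer", which gives about 15 per arm.

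The Statistical Analysis Plan does not mention antibody. For outcomes of this kind it says "Categorical data will be described with frequencies and percentages and compared using Fisher's exact or chi square tests". For measured quantities it says "Continuous data will be summarized by means and standard deviation (SD) and analyzed by student t tests". A p value under 0.05 "will be considered significant"; sidedness is not stated.

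Two further provisions bear on the point. In the Design section, after the exclusion criteria, "Subjects in the SoC only arm with deterioration of respiratory parameters and CSS markers at 48-96 hours will be transitioned to treatment with anakinra". In the visit schedule, blood draws run from Day 0 to Day 10 and include no antibody test. Follow-up is meant to go further: after study drug is stopped, "the subject will be followed for the full treatment/observation period (through Day 60").

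**The concern.** A neutralizing antibody level can be graded as a titre. Recording only whether any antibody developed keeps the extreme lower tail of that distribution. If a drug lowers every patient's titre, only those already near the detection limit cross it. A patient who stays positive at a much lower level counts the same as one who is unaffected.

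This is the only stated aim that asks whether anakinra harms antiviral antibody. At low power, a non-significant comparison could be read as reassurance although it carries little information. Supplying the missing Day 28 visit would not cure this, because the outcome would still be yes/no.

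**Working it through.** **Inputs from the documents:** 30 patients at 1:1, so 30/2 = 15 per arm; Fisher's exact or chi-square for categorical data; significance at 0.05. The plan states no power or effect size for any endpoint, so there is no figure of its own to reproduce.

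**Assumptions:** two-sided testing; normal log titre with equal SD in both arms; undetectable values tied at the limit; control failure p0 from 2% to 20%; no crossover in the base case.

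**Step 1: what Fisher needs.** With 15 per arm, 4 failures against 0 gives p = 0.100 and 5 against 0 gives p = 0.042. With one control failure, 6 against 1 gives p = 0.080 and 7 against 1 gives p = 0.035. With no control failures, a third of the anakinra arm (5/15) must show no antibody before the test responds.

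**Step 2: uniform fall of d SD.** Failure on anakinra is p1 = Φ(Φ⁻¹(p0) + d). For p0 = 5% and d = 1, this is Φ(−1.645 + 1) = Φ(−0.645) = 26%. Power of the yes/no tests is the sum, over all pairs of binomial counts, of their probability wherever p < 0.05 (chi-square without continuity correction). Power of the rank test is by simulation with titres floored at the limit. For d = 1:

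| Control failure | Fisher | Chi-square | Rank test on titre |
|---|---|---|---|
| 2% | 4% | 13% | 72% |
| 5% | 19% | 34% | 71% |
| 10% | 30% | 48% | 70% |
| 20% | 37% | 55% | 69% |

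Repeated simulation puts the rank-test column between about 67% and 73%. Chi-square is the less secure of the two yes/no tests: with equal arms, expected failures per arm are half the total, so they fall below 5 whenever fewer than 10 patients fail. At p0 = 5% the expected total is 15 × (0.05 + 0.26) = 4.65. With 12 evaluable per arm at p0 = 5%, power is Fisher 10%, chi-square 23% and rank test about 59-61%.

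The gain is not always large. At 12 per arm, 20% control failure and a 0.5 SD fall, it is 14% (chi-square) against 19% (rank test).

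**Step 3: in fold terms.** An SD must be assumed. If the log10 SD is 0.4 to 0.8, a 1 SD fall is 10^0.4 = 2.5-fold to 10^0.8 = 6.3-fold. Here d = log10(fold)/SD. With SD 0.5 and p0 = 5%:

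| Loss | d | Fisher | t test on log titre |
|---|---|---|---|
| 3-fold | 0.477/0.5 = 0.95 | 16% | 71% |
| 4-fold | 0.602/0.5 = 1.20 | 35% | 89% |
| 5-fold | 0.699/0.5 = 1.40 | 53% | 96% |

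Over SD 0.4-0.8 and p0 of 1-10%, Fisher power is below 50% in all 12 cells for a 3-fold loss and in 30 of 36 cells for 3- to 5-fold losses. At SD 0.8 the t test itself has only 35%, 51% and 64%.

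**Step 4: a different effect shape.** Suppose anakinra makes a fraction f non-responders and leaves the rest unchanged, so p1 = p0 + (1 − p0)f. With 15 per arm:

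| p0 | f | p1 | Fisher | Chi-square | Rank test |
|---|---|---|---|---|---|
| 5% | 30% | 0.05 + 0.95 × 0.30 = 33.5% | 36% | 54% | 26% |
| 5% | 40% | 0.05 + 0.95 × 0.40 = 43% | 59% | 76% | 42-44% |
| 2% | 40% | 0.02 + 0.98 × 0.40 = 41.2% | 70% | 84% | 45% |

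The ranking reverses.

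**Step 5: crossover.** The rate is not stated; take 30%, with crossed-over controls receiving the full 1 SD fall. At p0 = 5%, control failure becomes 0.7 × 5% + 0.3 × 26% = 11.3%. Fisher falls to 8% and the rank test to about 40%.

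**The case against.** The strongest reply is that sub-aim 8 names failure to develop antibody, which is a harm in itself. The documents nowhere say that a lower but present titre matters. If the harm is that some patients do not respond, Step 4 shows the yes/no comparison is the better test. This stands. A reader might infer that titre should replace the failure proportion, with the latter reported only descriptively. The documents do not support that, because it would give up power for the very harm the protocol names.

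A reader might also infer that the yes/no analysis would nearly always show no difference. That is too strong. Chi-square reaches 48-55% at 10-20% control failure for a 1 SD fall. Fisher reaches 62-72% for a 4-fold loss and 81-87% for a 5-fold loss if the log10 SD is 0.4 and 5-10% of controls fail.

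Nor can it be said that the trial's own samples would have revealed the loss. The schedule lists no Day 28 draw and no assay is named, so it is unknown whether a titre would exist.

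Finally, the SAP already has a t test for continuous data, and assigning this outcome to Fisher or chi-square is an inference from the aim's wording. That is fair, but a test for continuous data helps only if titre is named as an outcome, and it is not.

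**Conclusion.** The concern holds in limited form. As worded, sub-aim 8 discards graded information. If anakinra lowers titres generally by about 1 SD, power with 15 per arm is 4-37% (Fisher) or 13-55% (chi-square), against about 67-73% for a rank test on titre. These figures rest on assumed normal log titres, a uniform shift, 2-20% control failure and no crossover; none of these comes from the plan. Under a subset-non-responder effect the yes/no test is better, so the two analyses complement each other. Thirty percent crossover would leave even the rank test at about 40%.

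The aim also reads as a no-harm statement without a margin, and a non-significant test cannot establish that. Even 0 failures in 15 on anakinra leaves a one-sided 95% upper limit of 1 − 0.05^(1/15) = 18%, or 22% as the upper end of a two-sided interval (1 − 0.025^(1/15)).

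This is a worthwhile, inexpensive addition to a secondary outcome.

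**What to change.** Keep the between-arm comparison of the proportion failing to develop neutralizing antibody, by Fisher's exact test, with the difference and its 95% CI. Add to sub-aim 8 and to the SAP:

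*Neutralizing antibody titre at Day 28 will also be compared between arms by Wilcoxon rank-sum with undetectable values ranked lowest, with the geometric mean titre ratio and 95% CI (censored-normal model if values are undetectable).*

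State in the SAP that a non-significant result on either comparison will not be reported as showing no impairment, and that both will be interpreted in light of the number of controls who crossed over.

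The cost is a few sentences and no added patients. The laboratory must report a titre on the Day 28 specimen, and one more secondary comparison is reported. Sub-aim 8 already requires that specimen, but the visit schedule does not list the draw and must do so for either analysis to be possible.
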